- Group 1: SC ramucirumab 350 mg (1 injection of 2 mL×175 mg/mL)
- Group 2: SC ramucirumab 700 mg (2 injections of 2 mL×175 mg/mL)
- Group 3: IV ramucirumab to a maximum of 350 mg (60-minute IV infusion; maximum 35 mL×10 mg/mL)
- Group 4: SC ramucirumab 350 mg (2 injections of 2 mL×87.5 mg/mL)
- Group 5: SC ramucirumab 350 mg (2 injections of 1 mL×175 mg/mL)
- Optional Group 6: SC ramucirumab (maximum planned dose level, 350 mg, given as slow SC infusion).

Groups 4 and 5 are planned to investigate single SC ramucirumab dose of 350 mg with different volume of injection (2 injections of 1 mL×175 mg/mL) and different concentration of the drug product (2 injections of 2 mL×87.5 mg/mL) compared to the first group dosed at 350 mg (1 injection of 2 mL×175 mg/mL). Data from these groups will provide insight about the effect of injection volumes and ramucirumab concentration on the PK and tolerability of SC ramucirumab.

The initial dose planned for Groups 3 and 6 are to be modified based on emerging data discussed at the safety review between sponsor and investigator (see Section 4.3 for rationale).

More precisely, following the emerging data from Groups 1 and 2, the study doses are modified downwards. This is pending the full safety review of all data from Groups 1 and 2. The IV dose (Group 3) will not exceed 350 mg, and the subsequent SC doses will be capped at 350 mg (Groups 4 through 6). In Section 4.3 (Justification for Dose), Groups 1 and 2 safety data justifying that change are presented in more detail.

Disclosure Statement: This is a PK and safety study to test both the marketed ramucirumab IV formulation and a novel ramucirumab SC formulation in healthy participants with the objective of comparing PK exposure and safety following both routes of administration.

Number of Participants:

Approximately 60 participants will be enrolled and randomly assigned to study intervention to obtain at least 48 evaluable participants for an estimated total of at least 8 evaluable participants per intervention group (Section 9.2).

Intervention Groups and Duration:

Participants will be screened within 28 days prior to Day 1 of dosing for each group. Within each group, participants will be randomized to receive a single dose of IV or SC ramucirumab or placebo (7 ramucirumab:3 placebo per group).

The dosing groups or treatment intervention are as stated in the study design:

[figure not shown]
- Group 1: SC ramucirumab 350 mg (1 injection of 2 mL×175 mg/mL)

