The data generated by the proposed Study I4T-MC-JVDT (JVDT) will be used to recommend a subcutaneous (SC) dosing regimen for ramucirumab to be used in further clinical development with the expectation to improve patient outcomes by changing the pharmacokinetic (PK) profile, relative to IV dosing, as follows:

- achieve and maintain higher trough concentrations (C_{trough}) with lower peak concentrations (C_{max}) while producing comparable overall exposure at steady state as the IV formulation (10 mg/kg every 2 weeks [Q2W] IV),
- increase the proportion of patients achieving target C_{trough} ($>50 \mu\text{g/mL}$), and
- with an initial loading dose, ensure $C_{trough} >50 \mu\text{g/mL}$ is achieved quickly in therapy.

This protocol will study both IV and SC ramucirumab in healthy participants to establish PK and safety after single-dose administration.

Section 2.1 and Section 4.3 provide more details about the study rationale, and dose justification and margin of safety, respectively.

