
 • Evaluate ramucirumab safety following a single dose in healthy participants • Assess ISRs following SC administration of ramucirumab using ISR questionnaire • Assess ramucirumab PK following a single dose of IV or SC administration 	
 • Incidence of AEs, TEAEs, and serious adverse events (SAEs) after IV administration and SC administration in healthy participants • Characterization and measurement of incidence and severity of ISRs (including injection site pain) using data collected from the ISR questionnaire • PK parameters: 
 ○ IV: area under the concentration versus time curve (AUC) from zero to infinity ($AUC_{[0-\infty]}$), maximum drug concentration (C_{max}), time of maximum concentration (t_{max}) ○ SC: $AUC_{(0-\infty)}$, C_{max}, t_{max} after SC administration

Exploratory	

 • Immunogenicity • Assess ISRs following SC administration of ramucirumab using Scarletred tool 	
 • The frequency and percentage of participants with preexisting antidrug antibodies (ADA) and with treatment-emergent antidrug antibody positive (TE ADA+) to ramucirumab will be tabulated and any difference after IV administration versus SC administration • For the TE ADA+ participants, the distribution of maximum titers will be described. The frequency of neutralizing antibodies will also be tabulated in TE ADA+ participants • The relationship between the presence of antibodies and the PK parameters, including safety, to ramucirumab after IV versus SC administration • Characterization and measurement of incidence and severity of ISRs using data collected from the exploratory tool

4. Study Design

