## 9.3 Pharmacokinetic Assessment

### 9.3.1 Pharmacokinetic Analysis

PK parameter estimates will be determined using non-compartmental procedures in validated software program (Phoenix WinNonlin Version 8.1 or later).

Plasma concentrations of ramucirumab (LY3009806) will be used to determine the following PK parameters, when possible:

Parameter	Units	Definition
AUC(0-t last )	h*μg/mL	area under the concentration versus time curve from time zero to time t, where t is the last time point with a measurable concentration
AUC(0-∞)	h*μg/mL	area under the concentration versus time curve from time zero to infinity
%AUC(t last-∞ )	%	percentage of AUC(0-∞) extrapolated
C max	μg/mL	maximum observed drug concentration
t max	H	time of maximum observed drug concentration
t 1/2	H	half-life associated with the terminal rate constant (λz) in non-compartmental analysis
CL/F	L/h	apparent total body clearance of drug calculated after extra-vascular administration
CL	L/h	total body clearance of drug calculated after intravenous administration
V Z /F	L	apparent volume of distribution during the terminal phase after extra-vascular administration (SC administration only)
V Z	L	volume of distribution during the terminal phase after intravenous administration (IV administration only)
V ss /F	L	apparent volume of distribution at steady state after extra-vascular administration
V ss	L	volume of distribution at steady state following intravenous administration
F	%	bioavailability based on AUC(0-∞)
		$F = \frac{AUC [SC]}{AUC [IV]} \times 100$

Additional PK parameters may be calculated, as appropriate.

---

The software and version used for the final analyses will be specified in the CSR. Any exceptions or special handling of data will be clearly documented within the CSR.

Formatting of tables, figures and abbreviations will follow the Eli Lilly Global PK/PD/TS Tool: NON-COMPARTMENTAL PHARMACOKINETIC STYLE GUIDE. The version of the tool effective at the time of PK analysis will be followed.

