### 9.3.2 Pharmacokinetic Statistical Methodology

Ramucirumab bioavailability will be estimated. PK parameters will be evaluated to estimate ramucirumab  $AUC_{(0-\infty)}$  and  $C_{max}$  dose proportionality following SC administration in the dose range investigated. Log-transformed ramucirumab  $C_{max}$  and  $AUC_{(0-\infty)}$  parameters will be evaluated in a linear mixed effects model with fixed effects for dose (Groups 1, 4, and 5 who received 350 mg will be combined if appropriate). The treatment differences will be back-transformed to present the ratios of geometric means and the corresponding 90% confidence interval.

For ramucirumab SC dosing PK parameters, the  $t_{max}$  will be analyzed using a Wilcoxon rank-sum test. Estimates of the median difference based on the observed medians, 90% CIs, and p-values from the Wilcoxon test will be calculated to assess similarity or not in  $t_{max}$  between dose level groups 1, 4, 5 combined compared to group 2 and group 6.

The above-mentioned analysis investigating the relationship (e.g. linearity/proportionality) between ramucirumab PK parameters and dose may be adjusted/repeated in the event of significant difference in PK between the 350 mg SC groups (Group 1, 4, 5). Such difference would indicate significant impact of either injection volume or drug product concentration on the PK. In this scenario, the analysis, investigating the relationship (e.g. linearity/proportionality) between ramucirumab PK parameters and dose, may be repeated by excluding the data from one or two of the 350 mg SC group.

Comparison of  $AUC_{(0-\infty)}$ ,  $C_{max}$  and  $t_{max}$  between Group 1 and Group 4 will enable to assess the effect of changing the drug product concentration on the exposure. The log-transformed  $AUC_{(0-\infty)}$ ,  $C_{max}$  and  $t_{max}$  will be the response variable, and the drug product concentration (that is, Group 1 and Group 4) is the explanatory variable.

Comparison of  $AUC_{(0-\infty)}$ ,  $C_{max}$  and  $t_{max}$  between Group 1 and Group 5 will enable to assess the effect of changing the volume injected at one site of injection on the exposure. The log-transformed  $AUC_{(0-\infty)}$ ,  $C_{max}$  and  $t_{max}$  will be the response variable, and the volume injected (that is, Group 1 and Group 5) is the explanatory variable.

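### Comparing PK exposure by route is a stated objective, but the SAP specifies no SC/IV contrast with an interval, and its only route quantity, F, has no estimator or dose normalisation

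*Protocol*

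**What the plan says.** The Disclosure Statement in Protocol 1.1 gives the study as one "with the objective of comparing PK exposure and safety following both routes of administration". The corresponding primary objective in Protocol Section 3 is "Assess ramucirumab PK following a single dose of IV or SC administration", with AUC(0-∞), Cmax and tmax as endpoints for each route.

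SAP 9.3.1 lists AUC(0-tlast), AUC(0-∞), percentage extrapolated, Cmax, tmax, half-life, clearance, volumes and F. F is defined as AUC[SC]/AUC[IV] × 100. The list closes with "Additional PK parameters may be calculated, as appropriate".

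SAP 9.3.2 opens with "Ramucirumab bioavailability will be estimated" and says no more about F. It then sets out a model for "dose proportionality following SC administration in the dose range investigated", a tmax comparison among SC groups, and comparisons of Group 1 with Group 4 and Group 1 with Group 5.

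Protocol Section 2 says the data "will be used to recommend a subcutaneous (SC) dosing regimen for ramucirumab to be used in further clinical development", with the expectation that the regimen will "achieve and maintain higher trough concentrations (C_{trough}) with lower peak concentrations (C_{max", at comparable steady-state exposure to 10 mg/kg IV every two weeks. The same section then limits the trial: "This protocol will study both IV and SC ramucirumab in healthy participants to establish PK and safety after single-dose administration". Protocol 9.4.2.1 states as a firm commitment that a non-linear mixed-effects analysis of the study's PK data will be done. The SAP does not mention it. SAP Section 3 says the SAP supersedes the protocol's statistical section, and SAP Section 11 declares no changes.

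**The concern.** Followed as written, the SAP gives separate Cmax, tmax and AUC summaries for IV and SC, and a figure for F. The reader gets no estimate with an interval for how peak or total exposure differs by route, although comparing exposure by route is a stated purpose and Group 3 exists to provide the reference.

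F itself is under-specified in two ways. Each participant receives one route, so F cannot be a within-person ratio; the SAP must say how group AUCs are combined, and it does not. The printed formula also has no dose term, although SC doses differ (350 and 700 mg) and Group 3 has only a maximum of 350 mg, with lower doses allowed.

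The analysis suited to the regimen question in Section 2, the mixed-effects model, is promised in one document and absent from the other.

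**Working it through.** **1. Figures in the plan that can be reproduced.** Sample size: 6 × 10 = 60 enrolled and 6 × 8 = 48 evaluable, not based on power. Appendix 6 SC/IV ratios of medians: first-two-week Cmax 141/206 = 0.68 and 134/206 = 0.65; steady-state trough 170/77 = 2.21 and 157/77 = 2.04. All agree with the printed values.

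**2. Where the IV group enters SAP 9.3.2.**

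| Analysis | Groups | Interval specified |
|---|---|---|
| Dose proportionality, Cmax and AUC | SC doses; 1, 4, 5 combined if appropriate | 90% CI |
| tmax, Wilcoxon | 1, 4, 5 combined v 2 and 6 | 90% CI |
| Product concentration | 1 v 4 | none in text |
| Injected volume | 1 v 5 | none in text |
| Bioavailability F | SC v IV (Group 3) | none |

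The example code has a single factor, dose, and no route or group term.

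**3. Dose term in F.** Under linear PK, AUC = F × D/CL for SC and D/CL for IV. The printed formula therefore returns

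printed F = true F × D(SC)/D(IV).

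For Group 2 against a 350 mg Group 3, at the protocol's assumed F of 0.6: 0.60 × 700/350 = 1.20, or 120%. For Groups 1, 4 and 5 the factor is 350/350 = 1 only if Group 3 receives its maximum; any lower IV dose inflates printed F in the same way.

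**4. Expected precision of an SC/IV ratio.** The documents give no SD for single doses in healthy participants. As an assumption, take log-SD = ln(P95/P5)/(2 × 1.645) from Appendix 6, using the IV every-two-weeks and SC twice-weekly columns:

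- Cmax: IV ln(285/153)/3.29 = 0.189; SC ln(227/87)/3.29 = 0.292.
- First-week AUC: IV ln(25.4/13.2)/3.29 = 0.199; SC ln(25.1/10.6)/3.29 = 0.262.
- Steady-state AUC, standing in for AUC(0-∞) under linear PK: IV ln(75/30)/3.29 = 0.279; SC ln(102/33)/3.29 = 0.343.

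The 90% limits are ratio ×/÷ exp(t × SE), with SE = √(s²(IV)/n(IV) + s²(SC)/n(SC)) and Welch degrees of freedom. For Cmax:

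- 7 v 7: SE = √(0.189²/7 + 0.292²/7) = 0.131; t = 1.81 (10.3 df); factor 1.27.
- 7 IV v 21 SC: SE = √(0.189²/7 + 0.292²/21) = 0.096; t = 1.74 (16.2 df); factor 1.18.

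The same steps give:

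| Quantity | 7 v 7 | 7 v 21 |
|---|---|---|
| Cmax | 1.27 | 1.18 |
| AUC(0-168h) | 1.25 | 1.18 |
| AUC(0-∞), i.e. F | 1.35 | 1.26 |

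With only six evaluable per arm, the Cmax factor is 1.30.

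For scale, the means in Protocol 4.3 imply a dose-normalised Cmax ratio of (139/1400)/(211/700) = 0.33. A 7 v 7 interval around that would run from 0.33/1.27 = 0.26 to 0.33 × 1.27 = 0.42. Small groups would still locate the ratio usefully.

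**5. Whether a single-dose trough ratio would answer Section 2.** Use the protocol's own inputs: distribution half-life 20 h, elimination half-life 10 to 14 days, a twofold fall by day 3, F = 0.6, absorption rate ka = 0.3/day. With α and β the two disposition rates:

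- IV: C = C0[A·e^(−αt) + B·e^(−βt)]; the twofold fall gives A = 0.43 to 0.46, B = 1 − A.
- SC: C = F·ka·C0[A(e^(−αt) − e^(−ka·t))/(ka − α) + B(e^(−βt) − e^(−ka·t))/(ka − β)].

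Equal single doses give an SC/IV concentration ratio at 336 h of 0.76 (10-day half-life) to 0.71 (14-day). Adding up the same curves over repeated doses, 700 mg SC weekly against 700 mg IV every two weeks, gives steady-state troughs of 142 v 74 µg/mL (ratio 1.9) to 189 v 113 µg/mL (ratio 1.7); Appendix 6 prints 2.04. One set of curves yields a single-dose ratio below 1 and a regimen ratio above 1, because the SC regimen gives 1400 mg per two weeks against 700 mg and has a shorter interval.

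**The case against.** The strongest defence is that the trial is unpowered and descriptive (Protocol 9.1 and 9.2), and no listed endpoint goes unreported. AUC, Cmax and tmax are derived and summarised for both routes, mean profiles are plotted, and F is the route comparison that Protocol 2.1 itself announces. That stands, and it keeps the point modest. It does not supply an interval, an estimator for F or a dose term.

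A reader might infer more: that the analysis cannot answer the Section 2 question because no trough-type parameter is listed, or that a low SC concentration at Day 15 would contradict the flatter profile expected in Section 2.1. The documents support neither. The aim in Section 2 concerns a repeat-dose regimen, and step 5 shows that a single-dose ratio below 1 is what the protocol's own assumptions predict alongside higher regimen troughs. Peak can be read descriptively by route, and Protocol 9.4.2.1 promises a model that could project steady-state trough and peak.

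Nor does the SAP's silence show that the model was dropped. Protocol 9.4.5 allows population PK to be reported outside the study report, and SAP Section 11 declares no change. What remains is that neither document says where that model is specified or names trough and peak as its outputs.

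The safety-margin table in Protocol 4.3 uses AUC over 168 h, but at the originally planned maximum doses, so an observed partial AUC would not be directly comparable with it.

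**Conclusion.** The point holds as a gap in specification. The route comparison named in the synopsis has no SC/IV ratio with an interval, and F lacks an estimator, an interval and a dose term. The missing dose term alone would double printed F for Group 2 against 350 mg IV.

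The data could give a Cmax ratio to within about ×/÷1.18 (7 v 21) to ×/÷1.27 (7 v 7), with F somewhat less precise. These factors assume that variability from a simulated patient population on repeat-dose regimens carries over to single doses in healthy participants; Protocol 4.2 says it is unknown whether clearance is similar in the two populations. The narrower figures also require pooling Groups 1, 4 and 5, which the SAP allows only if appropriate.

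The groups are enrolled sequentially or in parallel and are not randomised against each other, so any SC/IV ratio is descriptive. The trough and peak-to-trough aim of Section 2 is a matter for the model, not for a single-dose contrast.

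**What to change.** - SAP 9.3.1: define F as [AUC(SC)/dose(SC)] ÷ [AUC(IV)/dose(IV)] × 100, using doses actually given. Add AUC(0-168h) as a descriptive partial AUC.
- SAP 9.3.2: add dose-normalised SC/IV geometric mean ratios with 90% CIs for Cmax, AUC(0-∞) (this ratio is F) and AUC(0-168h), for Groups 1, 4 and 5 each against Group 3, and combined only if pooling is appropriate. Estimate them from a log-scale model with a group term that includes Group 3 and lets the variance differ by route. Label the ratios descriptive and say why.
- Mixed-effects model: describe it in the SAP, or cross-refer to its own plan, with steady-state trough and peak by route as named outputs.
- Concentrations at 168 h and 336 h may be listed, with a note that they do not test the Section 2 aim.

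The cost is SAP wording and one table. Both routes are already sampled at 168 h and 336 h (Protocol 1.3.1), so no extra blood is drawn. The downside is a few more descriptive intervals, some of them wide.

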2.1. Study Rationale

Ramucirumab presents a biphasic disposition PK following IV administration, with a distribution apparent terminal elimination half-life ($t_{1/2}$) of approximately 20 hours and elimination $t_{1/2}$ of approximately 10 days to 2 weeks. Consequently, there is an initial 2-fold decline in ramucirumab concentration during approximately the first 3 days postdose before reaching the terminal phase where the ramucirumab concentration declined more slowly.

Hence, there may be an opportunity to optimize the ramucirumab PK profile using an SC formulation. An SC formulation would enable ramucirumab to be absorbed over a longer period of time than the 60-minute IV infusion, leading to a more constant ramucirumab concentration over the dosing interval with a higher C_{trough} , lower C_{max} , and lower peak-to-trough ratio under SC administration compared to IV administration.

The clinical development of IV ramucirumab has been exclusively done in cancer patients. However, for the new proposed SC route of administration, the important biopharmaceutic

questions (such as PK and bioavailability) will be more efficiently investigated in the healthy human population (questions such as PK characteristics may be answered prior to formally investigating the efficacy of SC ramucirumab). The large clinical data with IV ramucirumab, together with the nonclinical toxicology data, support investigating single IV and SC doses of ramucirumab in a healthy human population. Section 2.3 (Benefit/Risk Assessment) and Section 4.3 (Dose Justification) provide details to support the clinical investigation of a single dose of ramucirumab in healthy participants.

This is a single-site study in healthy participants who will receive a single dose of SC or IV ramucirumab. The study will be participant- and investigator-blinded, randomized, and placebo-controlled (7 ramucirumab:3 placebo per group/dose level). Placebo will be used as a comparator for both IV and SC to allow interpretation of safety and tolerability data following administration. Section 1.2 provides the study schema. Section 4.1 presents the study design and the different group/dose levels.

The study will provide the critical SC ramucirumab PK area under the concentration versus time curve (AUC) data to enable the determination of the bioavailability by comparison to the AUC following IV administration. It will also help further clinical development in terms of choice of dosing regimen and administration condition (in particular by assessing the effect of changing the volume injected, or changing the concentration of SC ramucirumab solution on the exposure and/or tolerability). The SC ramucirumab dosing will consist of subsequent dose-escalation groups (up to 3 dose levels predicted to be ultimately used for therapeutic intent [see Section 4.3 for dose rationale]) to assess both safety and PK behavior (exposure and bioavailability).

2.2. Background

See Section 2 and Section 2.1.

2.3. Benefit/Risk Assessment

More detailed information about the known and expected benefits and risks and reasonably expected adverse events (AEs) of ramucirumab may be found in the Investigator's Brochure (IB).

The safety profile of ramucirumab given IV in adults with advanced cancers across a number of indications is well established. Adverse events of special interest (AESIs) identified for ramucirumab monotherapy include infusion-related reactions (IRRs), hypertension, proteinuria, arterial thromboembolic events (ATEs), bleeding/hemorrhage and gastrointestinal (GI) perforation. Analysis of Cycle 1 data from ramucirumab monotherapy Phase 3 studies in patients with advanced gastric and hepatocellular carcinoma showed the majority of TEAEs reported were reversible Grade 1 and 2 events, occurring at similar rates in both ramucirumab and placebo arms. The commonly reported TEAEs were hypertension, fatigue, abdominal pain, and anemia. In addition to hypertension, other AESIs reported were proteinuria, bleeding/hemorrhage events, and IRRs. Hypertension, anemia, and anaphylaxis were the events to be reported as Grade 3 events in the ramucirumab arm. Given that the duration of treatment in this study is a single dose, much shorter than the duration of treatment received by cancer patients, and the trial population is healthy, and therefore lacking risk factors for the majority of these events

(excluding IRRs), the risk to participants of experiencing these toxicities is reduced. These risks are considered manageable in a clinical research unit (CRU) setting and are mitigated in the protocol, as the participants will be closely monitored following the single-dose administration. This will enable prompt identification of AEs and treatment as needed. Premedication is also considered to help reduce the severity of potential immediate cutaneous reactions.

The nonclinical safety profile of IV-administered ramucirumab has been evaluated in repeat-dose toxicity studies of up to 39-weeks duration in cynomolgus monkeys. The local irritation potential of a single SC administration of ramucirumab, as formulated for presentation in this clinical protocol, has also been evaluated in monkeys. Taken together, the results of these studies support the safe administration of single SC doses of ramucirumab in this protocol, with exposure-based safety margins of 11X to 12X with respect to the maximum planned dose (see Section 4.3 for details).

More precisely, in nonclinical repeat-dose studies, IV ramucirumab was well tolerated and no adverse effects were observed after once-weekly (QW) administration of ramucirumab doses up to 40 mg/kg in a 5-week study, or after 11 weekly administrations of doses up to 50 mg/kg in a 39-week study in cynomolgus monkeys. Section 4.3 presents the margin of safety of the highest proposed single IV and SC ramucirumab dose in Study JVDT relative to the nonclinical no-observed-adverse-effect level (NOAEL) in the 5-week monkey study.

In the 39-week study in monkeys, renal toxicity and effects on the epiphyseal growth plate were observed. Because these effects emerged only after a long duration of repeated exposures, they are not expected following a single dose in this trial.

In the single-dose study of ramucirumab administered SC in monkeys, doses of up to 10-mg/kg ramucirumab were well-tolerated with no clinical signs or gross evidence of injection site reactions (ISRs). Non-adverse effects consisting of minimal fibroblast hypertrophy at >1 mg/kg, and minimal macrophage infiltrate at 10 mg/kg, were observed microscopically at the injection site; these effects are expected outcomes of introduction of foreign protein into the SC space and indicate a low potential for irritation at the injection site.

Because ramucirumab is a biotherapeutic, no genotoxicity studies have been conducted. No genotoxicity is expected based on the mechanism of action. No reproductive toxicity studies have been conducted. Based on the mechanism of action, fetal harm would be expected and therefore in this study, women of childbearing potential (WOCBP) are excluded and male participants with partners of childbearing potential must use contraception for the required time period to mitigate this risk.

There is no anticipated therapeutic benefit for the participants in this trial. However, participants may benefit from the screening procedures (through detection of unknown health issues) even if they receive no therapeutic benefit from the trial.

3. Objectives and Endpoints

Objectives	Endpoints
Primary	

 • Evaluate ramucirumab safety following a single dose in healthy participants • Assess ISRs following SC administration of ramucirumab using ISR questionnaire • Assess ramucirumab PK following a single dose of IV or SC administration 	
 • Incidence of AEs, TEAEs, and serious adverse events (SAEs) after IV administration and SC administration in healthy participants • Characterization and measurement of incidence and severity of ISRs (including injection site pain) using data collected from the ISR questionnaire • PK parameters: 
 ○ IV: area under the concentration versus time curve (AUC) from zero to infinity ($AUC_{[0-\infty]}$), maximum drug concentration (C_{max}), time of maximum concentration (t_{max}) ○ SC: $AUC_{(0-\infty)}$, C_{max}, t_{max} after SC administration

Exploratory	

 • Immunogenicity • Assess ISRs following SC administration of ramucirumab using Scarletred tool 	
 • The frequency and percentage of participants with preexisting antidrug antibodies (ADA) and with treatment-emergent antidrug antibody positive (TE ADA+) to ramucirumab will be tabulated and any difference after IV administration versus SC administration • For the TE ADA+ participants, the distribution of maximum titers will be described. The frequency of neutralizing antibodies will also be tabulated in TE ADA+ participants • The relationship between the presence of antibodies and the PK parameters, including safety, to ramucirumab after IV versus SC administration • Characterization and measurement of incidence and severity of ISRs using data collected from the exploratory tool

4. Study Design

